Historically, other methods were used to combat post-operative pain. Buchko et al looked at intra-articular analgesia after arthroscopic ACL reconstruction and found an increased rate of chondrolysis, which was similar to other studies that looked at its use in the shoulder joint (11). Use of peripheral nerve blockade is not new practice and has been described throughout the literature. Manickam et al showed 100% success rate and full blockade after twenty minutes with use of the adductor canal block (12). The safety and efficacy of the Continuous Peripheral Nerve Block (CPNB) has been thoroughly investigated. Carvhalo et al found that the addition of a peripheral catheter added only 10 minutes to procedural time versus single shot peripheral nerve block (14). In a group of 35 trauma patients it was found that despite continuous peripheral nerve infusion, serum levels of Ropivacaine were well below toxic levels (15). A review article by Nicolotti et al found that the incidence of positive cultures of placed catheters varied widely from 6%-57%, but the actual incidence of positive cultures resulting in clinical infection was 0%-3.2% (13). The large discrepancy between the two values was found to be likely due to inadequate skin preparation and improper technique with removal.

Some studies have shown the efficacy of CPNB use and concluded with positive results. A multicenter prospective study of use of CPNBs found high quality postoperative pain reduction along with low rates of neurologic or infectious complications (1) and according to Enneking et al. CPNBs have been shown to improve patient satisfaction and improve rehabilitation compared to IV narcotics after orthopedic surgery for both upper and lower extremity (3). A more recent study prospectively looked at CPNB vs placebo (Normal Saline) performed in the upper extremity and found that there was a statistically significant reduction in pain, opioid use, sleep disturbances and increase in patient satisfaction scores (4). A large meta analysis by Richman et al looked at the efficacy of CPNBs and found statistically significant reduction in opioid use, pain up to 72 hours postoperative and decrease in episodes of nausea and vomiting (5) with use versus opioid analgesia.

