Outcomes measured on post-operative days 1,2,3,4,7, and at the post-operative follow-up visit.

- Quality of Sleep
 - Trouble falling asleep due to pain (yes,no)
 - Wake due to pain (yes,no)

Outcomes measured at post-operative follow-up visit

- Satisfaction with surgery, on a scale of 0 to 10, where 0 represents extremely dissatisfied and 10 extremely satisfied
- Adverse events: Adverse events will be assessed at each visit. At the end of the study, each subject will be categorized as having had one or more adverse events, or not having had any adverse events.
- Serious Adverse events: Serious adverse events will be assessed at each visit and via telephone on post-operative day 1, 2, 3, 4 and 7. At the end of the study each subject will be categorized as having had one or more serious adverse events, or not having had any serious adverse events.

Statistical Methods:

Primary Outcomes:

For each outcome, repeated measures analysis of variance (RMANOVA), where post-operative pain control method (bolus block, continuous catheter) is the between subjects effect and post-operative day is the within subjects effect will be used to examine the association between pain control method and that outcome. Site (stratification variable) will be included as a covariate in each model. The interaction of post-operative control method and day will be included in the model. If the interaction is significant, then pairwise comparisons of pain control method at each day will be carried out within the RMANOVA model. If the usual assumptions required for the ANOVA model are not met, then a suitable transformation, or an appropriate non-parametric method will be used.

Secondary Outcomes:

For binary outcomes measured on days 1,2,3,4,7 and 10:

For each outcome, a generalized linear mixed model (GLMM) for binary clustered (i.e., hierarchical) data will be used to examine the association between pain control method and that outcome. GLMM will be used to account for the hierarchical structure of the data, (namely, multiple days within a subject). Site (stratification variable) will be included as a covariate in each model.

For binary outcomes measured on day 10 only:

For each outcome, logistic regression will be used to examine the association between pain control method and that outcome. Site (stratification variable) will be included as a covariate in each model.

For satisfaction with surgery:

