16. WITHDRAWAL OF SUBJECTS

- *Describe anticipated circumstances under which subjects will be withdrawn from the research without their consent*
- *Describe procedures for orderly termination*
- *Describe procedures that will be followed when subjects withdraw from the research, including partial withdrawal from procedures with continued data collection.*

Participants may withdraw voluntarily from the study at any given time with no reason as is outlined in the informed consent for participation in the study. Any participant who withdraws from a study arm will still be contacted for follow-up assessments as outlined within this protocol unless the participant elects to forgo follow-up contact with the study assessors. This will include the surveys for outcome assessment, phone calls made on the subsequent postoperative days and the office visit following surgery.

Discontinuation from the continuous administration of local anesthetic prior to completion of the medications' dosing will not be deemed a withdrawal from the study but rather a discontinuation of treatment and the participant will continue to be followed up with for assessment of study outcomes with notation of the discontinuation of treatment within the database and the reason for discontinuation documented.

All participants who discontinue intervention will be followed in order to assess for potential adverse events, serious adverse events and any unanticipated problems pertaining to the use or administration of the study medications.

Adverse events include but are not limited to block failure, allergy to local anesthetic, persistent pain at injection/catheter site, local skin irritation at catheter site, pump/device failure.

Should a participant experience any of the serious adverse events listed in the next section, this participant will immediately be halted from their study intervention. These patients will be recommended to seek immediate care for assessment of their serious adverse event to best ensure patient safety. Should a patient experience an adverse event or unanticipated event, the study investigator who is contacted will determine if the participant's event meets criteria for discontinuation of treatment.

ADVERSE EFFECTS OF TREATMENT

Risks associated with single shot adductor canal block

1. Peripheral Nerve Injury

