1. Both anesthetists and surgeons recognize the benefits of peripheral nerve catheters (PNCs). The continuous infusion of local anesthetic near a peripheral nerve or plexus produces fewer systemic side-effects than i.v. opioids, increases postoperative patient satisfaction, and can allow for faster functional recovery of the operated limb.
2. Block Failure
 - a. Occasionally, there are instances when the catheter is passed easily but the nerve block fails to provide adequate anesthesia or analgesia.
 - b. This is rare with the use of ultrasound guidance and localization of the continuous catheter.
 - c. In the event of a block failure or inadequate placement that is not providing the patient any relief, the catheter will be removed either by the patient or post operatively depending on when it is discovered.
 - d. The practicing anesthesiologist will discuss with the patient the option of either trying a second time to place the catheter successfully in the post anesthesia recovery area or discontinuing the block altogether.
3. Accidental Catheter Migration/Removal
 - a. The incidence of accidental catheter removal is reported in the literature at about 1%. The use of sterile adhesive tagaderm dressing has been implemented to firmly secure the catheter to the skin to avoid migration or fall out. The dressing is checked to be secure after it has been applied.
 - b. In the event that the catheter is accidentally removed or dislodged during the course of the study, it should be removed and there will be no further intervention once the patient has been discharged home. The patient can place a Band-Aid over the catheter site and notify the coinvestigator or PI.
4. Localized Infection
 - a. Localized inflammation is infrequent (0–10%), and local infection (0–3%), abscess formation (0–0.9%), and sepsis occur even more rarely.
 - b. Transparent dressings are used to reduce the number of dressing changes while appropriately monitoring the site for signs of inflammation
 - c. Since the continuous catheter remains in for 48-72 hours, it does pose a theoretical increased risk of infection compared to a single shot adductor canal block although this has not been proven in the literature. To minimize this risk the site is prepped in sterile fashion with either chlorhexidine or iodine scrub. The injecting physician washes hands and uses sterile gloves and instruments for the course of this procedure.

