18. RESEARCH RELATED HARM/INJURY

- *Describe the availability of medical or psychological resources that subjects might need as a result of anticipated problems that may be known to be associated with the research.*
- *If the research is greater than minimal risk, explain any medical treatments that are available if research-related injury occurs, who will provide it, what will be provided, and who will pay for it.*

Adverse events and planned interventions prior to discontinuation

- Failure of catheter placement despite successful administration of single site injection- any participant who was randomized to receive a continuous

pump, but the catheter was unable to be placed will be discontinued from the continuous pump protocol, however these patient's will continue to be followed according to the above stated protocol and their outcomes assessed in an intent-to treat manner based on their initial randomization.

- Continuous Block failure- if patient perceives no benefit from block but pump appears to be functioning patient will be requested to continue the pumps use until the medication dosing is completed, a perceived block failure will be documented.
- Allergy to local anesthetic- if a patient reports a systemic allergic response including but not limited to shortness of breath, diffuse rash, or angioedema the patient will be recommended to discontinue the intervention and seek emergency care. If the patient reports a local confined rash or skin irritation around the catheter site with no systemic symptoms the patient will be recommended to take a dose of Benadryl and apply a warm compress, if symptoms resolve the patient will remain in the study if there is no resolution the patient will be told to discontinue the medication administration and seek care for further evaluation.
- Persistent pain at catheter site- the patient will be advised to place a cold or warm compress at the catheter site and adjust the adhesive bandage if necessary if these interventions do not alleviate the participants pain within 12 hours the patient will be advised to discontinue the intervention.

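### The any-adverse-event comparison pools events either arm can have with events that need a catheter or pump, and no breakdown is planned

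*Combined protocol and SAP*

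**What the plan says.** Section 12 (Secondary Outcomes) says that, once follow-up is over, "each subject will be categorized as having had one or more adverse events, or not having had any adverse events". A separate yes/no outcome covers serious adverse events. For binary outcomes of this kind, "logistic regression will be used to examine the association between pain control method and that outcome", with site as a covariate. No breakdown by event type, relatedness or device is planned.

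Section 16 says what feeds the indicator. The list opens "Adverse events include but are not limited to block failure, allergy to local anesthetic" and continues "persistent pain at injection/catheter site, local skin irritation at catheter site, pump/device failure". Of the five named items, two need a catheter or pump as worded. Site pain is worded for either arm, and block failure and allergy can occur in either.

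Section 18, under a heading on adverse events, has five items, four of them worded for the catheter or pump. One is "Failure of catheter placement despite successful administration of single site injection". Another is failure of the continuous block, where "a perceived block failure will be documented". No parallel instruction covers a single-shot patient whose block fails. Sections 16 and 17 likewise discuss block failure only among the catheter risks.

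Section 12 also says that neither physicians nor patients can be blinded.

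**The concern.** An event that needs a device can only add to the catheter arm's count. A pump that stops without symptoms moves a patient from no to yes exactly as a nerve injury does. If more catheter patients have an event, the odds ratio cannot say whether they were harmed more or simply had equipment that could fail.

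Recording may add to this. Where an event that either arm can have is documented by instruction in one arm only, and the trial is open-label, ascertainment can differ by arm.

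Apart from the serious-event indicator, this odds ratio is the only planned between-arm safety comparison from 78 patients, so its meaning matters.

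**Working it through.** **The plan's own figure.** The documents give no sample size, event rate or significance level for adverse events. The figure that can be checked is 39 per group for pain (2-point difference, SD 2.5, two-sided 0.01, 80% power). A two-sample t-test with effect 2/2.5 = 0.8 needs 38.2, so 39 per group, with 81.0% power. It reproduces, but it was not chosen with safety in mind.

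**Inputs for the illustration.**
- From Section 12: 39 per arm.
- Assumed: two-sided 5%; shared-event risk s of 10% or 30%, the same in both arms; independence of shared and device-only events.
- Device-only risk d: 0, 1%, 5% and 11%. Section 16 gives about 1% for accidental catheter removal and 0–10% for localized inflammation. Combining the tops gives 1 − 0.90 × 0.99 = 0.109, or about 11%. This is a generous reading. It treats inflammation as wholly catheter-related, and accidental removal is not among the adverse events named in Section 16 or 18. In the other direction, no rates are given for pump or placement failure.

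**Formulas.** Catheter-arm total = 1 − (1 − s)(1 − d). Excess over single shot = d(1 − s). The chance of declaring a difference comes from exact binomial enumeration with a pooled two-proportion z-test. It stands in for the planned logistic model and ignores site.

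| s | d | Single shot | Catheter | Excess (points) | Odds ratio | Difference declared |
|---|---|---|---|---|---|---|
| 10% | 0 | 10% | 10.0% | 0 | 1.00 | 5.9% |
| 10% | 1% | 10% | 10.9% | 0.9 | 1.10 | 6% |
| 10% | 5% | 10% | 14.5% | 4.5 | 1.53 | 10% |
| 10% | 11% | 10% | 19.9% | 9.9 | 2.24 | 24% |
| 30% | 0 | 30% | 30.0% | 0 | 1.00 | 5.3% |
| 30% | 1% | 30% | 30.7% | 0.7 | 1.03 | 5% |
| 30% | 5% | 30% | 33.5% | 3.5 | 1.18 | 7% |
| 30% | 11% | 30% | 37.7% | 7.7 | 1.41 | 11% |

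For example, in the fourth row 1 − 0.90 × 0.89 = 0.199, and (0.199/0.801)/(0.10/0.90) = 2.24.

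**Net direction when shared risks differ.** Suppose shared events are 20% with single shot and 10% with the catheter, a difference of −10.0 points. The any-event difference is 1 − 0.90(1 − d) − 0.20: −9.1 points at d = 1%, −5.5 at 5%, −1.0 at 10% and +8.0 at 20%. It is zero at d = 1 − 0.80/0.90 = 11.1%. The push is always in the same direction. Whether it reverses the sign depends on rates the documents do not state.

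**The case against.** **The total is a legitimate comparison.** Device failure and catheter irritation are real consequences of choosing a catheter, and Section 12 analyses everyone by randomised arm. Any-event burden is therefore a valid intention-to-treat quantity. This stands: the total is a limited summary, not an invalid one, and it should stay.

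**Much of the list is shared.** Site pain is worded for injection or catheter site, block failure and allergy can occur in either arm, and the list is open-ended. Single-shot patients are also told to report redness or drainage at the injection site. This stands too, and it limits how much can be called device-only.

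**Some protection exists.** Serious events are analysed separately, and severity, duration and reasons for discontinuation are recorded, so a breakdown could be produced later. This stands in part. It protects the gravest events, but classifying the rest after the data are seen, in an open-label trial, would be open to challenge.

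**Stronger readings that a reader might infer.** One is that the catheter arm must look worse by construction. The documents do not support that: at 1% device-only events, a halving of shared events from 20% still shows as −9.1 points. Another is that a real fall in shared harms is being hidden. No hypothesis in Section 2 or 19 predicts fewer adverse events. The "decrease in episodes of nausea and vomiting" cited in Section 3 is against opioid analgesia, not single shot. Section 16 describes infection risk as theoretically higher with the catheter and notes a theoretical toxicity risk at home.

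**Conclusion.** The point holds as a problem of interpretation. The indicator mixes shared and device-only events, the mixture pushes the odds ratio against the catheter arm, and nothing planned would separate the two.

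Over the device-only range that can be built from the documents' own figures (about 1% to 11%, the top being generous), the chance of declaring a difference when shared risks are equal is about 6% to 24% at a 10% shared risk and 5% to 11% at a 30% shared risk. At the low end there is almost no inflation. Higher device-only rates are possible, because pump and placement failure are unquantified, but the documents do not support any particular figure.

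These results rest on assumed shared rates, an assumed 5% level and independence. A breakdown also does not rescue power: for 20% against 10% in shared events, 39 per arm gives about 23% by the normal approximation. The gain is in what the safety result means, not in its precision.

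**What to change.** In Section 12, keep the any-adverse-event comparison by randomised arm and pre-specify two components beside it.

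1. **Events possible in either arm:** any of block failure, pain at the block site, irritation or infection at the block site, allergy, nerve symptoms, local anesthetic toxicity, and other types not tied to the device. Record these by the same questions in both arms, including perceived block failure, and compare them with the same logistic model with site as a covariate.
2. **Catheter- and pump-specific events:** pump failure, placement failure and dislodgement, reported as counts with exact confidence intervals in the catheter arm, with no between-arm test. State which of these count toward the total.

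If the second component is also shown among patients who actually received a catheter, label it as a descriptive exception to the Section 12 rule that all analyses follow intention to treat.

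The cost is a few lines of Section 12, one coding column on the adverse event form, the same questions asked of both arms at contacts already planned, and one more table. No extra patients or visits are needed.

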12. STATISTICAL ANALYSIS

- *Describe how your data will be used to test the hypotheses.*
- *State clearly what variables will be tested and what statistical tests will be used.*

- *Include sample size calculations.*
- *If this is a pilot study, state which variables will be examined for hypothesis generation in later studies.*

Blinding:

Due to the nature of the intervention (bolus block, continuous infusion pump), it is not possible to blind the physicians or patients.

Consent:

Consent will be obtained during the preoperative visit, prior to surgery.

Randomization:

Subjects will be randomly assigned in a 1:1 ratio to either bolus block or continuous catheter. The randomization will be stratified by hospital (Plainview, Franklin, Huntington, Long Island Jewish, or North Shore University Hospital).

The Biostatistics Unit will develop a randomization procedure using a permuted block design within the Biostatistics Randomization Management System (BRMS).

Additional details of the procedure, including required record keeping, will be further developed upon approval of this protocol. The Biostatistics Unit has extensive experience in implementing and in producing detailed documentation for such procedures.

Intention to Treat (ITT):

All analyses will be carried out according to the ITT principle. The ITT population will be all subjects randomized, regardless of what treatment they actually received. All patients will be analyzed in the group to which they were randomized.

Statistical Considerations:**Specific Aims:**

To compare the efficacy of two postoperative pain control methods (bolus block, continuous catheter) in patients undergoing ACL reconstruction.

Primary Outcome

Outcomes measured on post-operative days 0, 1,2,3,4,7, and at the post-operative follow-up visit. (Outcomes for days 0, 1,2,3,4, and 7 will be obtained via email and electronic surveys . Outcomes for the post-operative follow-up visit will be measured during the postoperative visit which takes place between days 10 and 14. This will be referred to as "Day 10").

- Pain Control

- Maximum pain will be measured on a scale of 0 to 10, where 0 represents no pain and 10 represents the worst possible pain. Patients will report the maximum pain felt in the 24 hours
- Current pain will be measured on a scale of 0 to 10, where 0 represents no pain and 10 represents the worst possible pain.
- Daily opioid consumption (expressed as morphine equivalents).

Secondary Outcomes

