Analysis of variance (ANOVA) will be used to examine the association between pain control method and satisfaction with surgery. Site will be included as a covariate in the model. If the usual assumptions required for the ANOVA model are not met, then a suitable transformation, or an appropriate non-parametric method will be used.

Sample Size Justification:

In a published study of 85 patients undergoing arthroscopic shoulder surgery, patients were randomly assigned to catheter (43 patients) or single-shot block (42 patients) for postoperative analgesia. Median pain with movement on day 3, measured on a visual analog pain scale, 6 in the single-shot group and 4 in the catheter group. As there is limited information available regarding postoperative pain levels following ACL reconstruction, we will assume that the difference in pain levels between bolus block and continuous catheter will be similar (i.e. continuous catheter will be 2 points lower than bolus block). The standard deviation will be estimated as 2.5. This estimate was obtained by dividing the range (10-0) by 4.

The proposed analysis will examine pain levels over multiple days during the postoperative period. If a significant interaction between treatment and day is found, it will be of interest to determine which days differ. Although this comparison will be carried out within the ANOVA model, the 2 sided two sample t-test will be used for purposes of calculating the required sample size. A sample size of 39 subjects per group will yield 80% power to detect a 2 point difference between the two groups on any single day using a two sided two-sample t-test at the 0.01 significance level. The reason for applying this “Bonferroni-type” adjustment is that pairwise comparisons will be carried out for 6 different days, and with this number of statistical tests, it is more likely to find a significant difference at the nominal 5% level when one does not actually exist. Based on our experience, most, if not all patients return for the postoperative visit, and therefore, no adjustment for drop-out has been made. Therefore, the proposed sample size will be 78 subjects (39 for each treatment group). |

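### The repeated measures ANOVA for pain and opioid use has no stated covariance structure, sphericity correction or per-day error term, so its error rates are not controlled if variance or correlation changes over days

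*Combined protocol and SAP*

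**What the plan says.** Section 12, Statistical Methods, Primary Outcomes, names RMANOVA for each primary outcome. Pain control method is the between-subjects effect, and "post-operative day is the within subjects effect will be used to examine the association between pain control method and that outcome". Site is a covariate and the method-by-day interaction is in the model. The day-by-day comparisons are conditional on a significant interaction, in which case "pairwise comparisons of pain control method at each day will be carried out within the RMANOVA model".

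The occasions come from the Primary Outcome list in the same section: "Outcomes measured on post-operative days 0, 1,2,3,4,7, and at the post-operative follow-up visit". The last one is "measured during the postoperative visit which takes place between days 10 and 14" and is labelled Day 10. The list covers maximum pain, current pain and daily opioid consumption, so all three go through this model.

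The only provision for failed assumptions is: "If the usual assumptions required for the ANOVA model are not met, then a suitable transformation, or an appropriate non-parametric method will be used". Section 12 does not mention sphericity, an epsilon correction, a covariance structure, or which error term the per-day contrasts use. The Sample Size Justification gives one SD, 2.5, obtained as range divided by 4, and no SD for any particular day.

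**The concern.** Univariate RMANOVA takes its within-subjects tests as valid when all differences between days have the same variance (sphericity). Equal variances with equal correlation between any two days satisfy this. Seven occasions spread over 10 to 14 days of recovery make that doubtful: measurements a day apart usually correlate more than measurements ten days apart, and scores or opioid totals that approach zero usually vary less.

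Two things are at stake. The interaction test decides whether any per-day comparison is made, so an inflated interaction test opens that gate too often. The per-day contrasts, if they use one error pooled over days, have the wrong standard error on every day whose variance differs from the average. The early days matter most clinically, because "Since the continuous catheter remains in for 48-72 hours" (Section 16), and these are the days for which the plan has not fixed the error term.

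**Working it through.** **The plan's own figure.** Inputs from the Sample Size Justification: difference 2 ("continuous catheter will be 2 points lower than bolus block"), SD 2.5, two-sided alpha 0.01, power 80%. The normal approximation is n = 2(z0.995 + z0.80)²(SD/difference)² = 2 × (2.576 + 0.842)² × (2.5/2)² = 2 × 11.68 × 1.5625 = 36.5, so 37 per group. The exact noncentral t gives 79.8% power at 38 and 81.0% at 39. The stated 39 per group reproduces. It rests on a single-day t-test, not on a pooled RMANOVA error.

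**Set-up of the check.** Null trials with no treatment effect, 39 per group, 7 occasions, 8,000 trials per scenario, complete data, no site term. Correlation was either constant at 0.5 or AR(1) at 0.7 per occasion. SDs by day are assumptions, since the documents give none. Monte Carlo standard errors are about √(0.084 × 0.916/8000) = 0.3 percentage points near 8.4% and √(0.01 × 0.99/8000) = 0.1 points near 1%.

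**Interaction test.** The univariate F has 6 and 76 × 6 = 456 degrees of freedom. Rejection at nominal 5%:
- Constant correlation: 4.9-6.3% over the SD profiles below.
- AR(1) 0.7: 7.7-8.4%, including 8.4% with SD 2.5 on every day.
- With Greenhouse-Geisser: 4.4-4.9% throughout.

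A further run with equal SDs and correlation decaying at 0.7 or 0.85 per day gave 7.3-8.6% uncorrected. Inflation of this test therefore does not need SDs that change by day.

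**Per-day contrasts, pooled error.** The variance used is v = (MS between + 6 × MS within)/7, with Satterthwaite degrees of freedom. Its expectation is the mean of the seven day-specific variances. For a day with SD s and pooled SD p, the rejection rate at nominal 1% is approximately 2Φ(−2.576 p/s). Example, profile (b): p = 2.45, so day 0 (s = 2.8) gives 2Φ(−2.25) = 2.4%, and the last visit (s = 1.6) gives 2Φ(−3.95) = 0.01%. Simulated rates before the interaction gate:

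| Assumed SD, days 0, 1, 2, 3, 4, 7, last | Early days | Day 7 | Last visit |
|---|---|---|---|
| (a) 2.5 throughout | 0.8-1.2% | 0.9-1.2% | 0.8-1.1% |
| (b) 2.8, 2.8, 2.7, 2.6, 2.4, 2.0, 1.6 | 1.3-2.6% (days 0-3) | 0.2% | at most 0.01% |
| (c) 2.8, 2.8, 2.8, 2.6, 2.2, 1.6, 1.2 | 1.8-3.0% (days 0-3) | at most 0.01% | at most 0.01% |
| (d) 1.8, 2.2, 2.5, 2.5, 2.5, 2.3, 2.0 | 0.1% day 0, about 2% days 2-4 | 1.1-1.2% | 0.3% |
| (e) 1.5, 2.0, 2.3, 2.5, 2.5, 2.5, 2.5 | 0.02% day 0, 0.3-0.5% day 1 | 1.7-1.9% | 1.7-1.8% |

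A milder start, SD 2.5 on days 0-3 falling to 1.8 or 1.2, gives 1.4-2.6% on days 0-3. An assumed opioid profile with SD falling from 20 to 3 gives up to about 7% on days 0-1. Separate runs ranged from 5% to 8%.

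**With the gate, as the plan is written.** Requiring a significant uncorrected interaction first, false early-day rates under the global null are about 0.3-1.9% for pain and about 3-6% on days 0-1 for the opioid profile.

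**After correction.** Using each day's own variance, per-day rejection at nominal 1% is 0.7-1.2% on every day in every scenario in the table.

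**The case against.** The strongest reply is that the plan never says a pooled error will be used. A multivariate repeated measures analysis, or a repeated measures model with a chosen covariance structure, would also fit the wording, and neither forces one variance on all days. That stands: the pooled error is the conventional reading of RMANOVA, not a quoted commitment. It changes the charge from an error to an unspecified choice, which could then be made after the data are seen.

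The assumption-failure clause also counts for something. Equal variance is among the usual assumptions, and a transformation can reduce a spread that shrinks with the mean. But the clause names no trigger or specific method, and neither remedy is aimed at correlation between days, which drives the interaction result.

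Three stronger readings are tempting, and the documents do not support them:
- A reader might infer that a false early benefit is about twice as likely as 1%. For pain that is the ungated rate under falling SDs. With the gate it is about 0.3-1.9%, and these two-sided rates count errors in both directions. The gate protects less if a real effect exists on other days.
- A reader might infer that late days have almost no chance of a finding. A low null rejection rate is not low power. In the pain scenarios falling from 2.5 to 1.8 or 1.2, power for the planned 2-point difference at 0.01, before the gate, was 92-98% on day 7 and 93-99% at the last visit.
- A reader might infer that the interaction test errs differently by day. It is one global test with one error rate.

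**Conclusion.** The concern holds as a gap in specification with a real effect on error rates under the conventional reading. The firmer part is the interaction test: about 7-9% at nominal 5% when correlation decays with time, whether or not SDs change. The per-day part is conditional. Pooled contrasts are off whenever SDs differ by day: too liberal on high-variance days and too conservative on low-variance ones. Falling SDs put the excess on early days, equal SDs remove it and rising SDs reverse it. The plan contains nothing that settles which applies. The largest effect is for the assumed opioid profile, which stays at about 3-6% on days 0-1 after the gate.

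These sizes rest on assumed SDs and correlations, normal errors, complete data and no site term. Confidence is moderate. The sample size is not in question.

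**What to change.** In Section 12, replace RMANOVA for the primary outcomes with a linear mixed model for repeated measures: treatment, categorical day, treatment-by-day and site, with unstructured covariance across days and Kenward-Roger degrees of freedom. Take both the interaction test and the per-day contrasts from that model. Name a heterogeneous Toeplitz structure as the fallback if it does not converge.

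If RMANOVA is kept, state that the interaction uses the Greenhouse-Geisser correction and that each day's contrast uses that day's own variance.

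The cost is SAP wording; n stays at 39 per group. The one drawback is 7 × 8/2 = 28 covariance parameters from 78 patients, hence the named fallback. A side benefit is that the mixed model uses the available days of a patient who misses a survey, which suits the intention-to-treat statement in Section 12 and the undertaking in Section 16 to account for single missed days in the analysis. The plan already uses mixed models for its repeated binary outcomes.
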